4.1.2. Sample Size Re-estimation

Not applicable for this study.

4.2. Randomization

At least thirty-two (32), maximum 36, subjects will be randomized, and as this is a multi-center study, centralized randomization will be performed. Treatment assignment will be randomized by blocks of 4 in sequential cohorts, with subjects assigned to either INP103 with or without carbidopa, or placebo delivered via the POD device with one, two, or four actuations, depending on cohort. Ratio of active to placebo assignment is 3:1. Randomization may occur on the day prior to (Day-1) or day of (Day-0) Visit 3 dosing. Subjects who are randomized but not dosed may be replaced at the Sponsor's discretion.

| Cohort | Treatment (Study Drug) |
|--------|--|
| 1 | INP103 35 mg L-dopa (n=6); Placebo (n=2) |
| 2 | INP103 70 mg L-dopa (n=6); Placebo (n=2) |

CONFIDENTIAL AND PROPRIETARY

| | |
|---|---|
| 3 | INP103 140 mg L-dopa (n=6); Placebo (n=2) |
| 4 | INP103 70 mg L-dopa/7.0 mg carbidopa (n=6, maximum 9); Placebo (n=2, maximum 3) |

For more detail, please refer to final Randomization Plan and Specification (version 3.0, dated: 22 FEB 2019).

4.3. Clinical Assessments

All clinical assessments are detailed in protocol amendment v4.0 (dated: 01 February 2019) Section 7. Study Schedule.

5. PLANNED ANALYSES

5.1. Interim Analyses

An interim analysis (IA) will be completed after Cohorts 1 and 2. Cohorts 1 and 2 data will be soft-locked and a subset of tables and listings will be provided. Subject level treatment allocations will not be provided to the sponsor. The aim of this analysis is to generate preliminary safety, efficacy and PK information from Cohorts 1 and 2 only.

To maintain the overall blinding of this study in the first instance, the IA tables and listings will be provided in the following way:

- For the specified demographic/baseline, adverse event and other safety listings, treatment will not be included/printed in the presentation. Data for the specified demographics/baseline and adverse events will be summarized by Cohort only, with data from active subjects and placebo subjects pooled for each cohort.
- For the specified efficacy listings, treatment will not be included/printed in the individual subject listing presentations. Data for the specified efficacy measures will be analyzed by an unblinded statistician and will be summarized by treatment for summary tables. Only summary statistics that do not allow the identification of individual patient level data will be presented (e.g. mean, SD). The summary statistics acceptable for presentation will be determined by the unblinded statistician based on comparison of the summary result values with individual subject data.
- For the specified PK data, only summary tables and figures will be produced. Data will be analyzed by an unblinded pharmacokineticist and will be summarized by treatment. No individual subject level data will be presented.

After review of the blinded IA results, it may be determined by the sponsor that the information provided is insufficient for the purposes of assessing safety, updating the study design for future cohorts, planning of future studies and/or reporting to various regulatory authorities and stakeholders. In this instance, and as described in protocol v3.0 (date: 26Jul2018), the sponsor is able to request the interim results be unblinded.

Unblinding of Cohort 1 and 2 will not bias the Cohort 3 dose escalation process or data collection. The soft-locked data for Cohorts 1 and 2 will not be modified based on the results observed from any unblinded IA data presentations. Any enrolled Cohort 3 subjects at the time of the IA will remain blinded at IA. The IA is for information only, and no formal trial stopping rule is set up at the IA.

All tables, listings and figures which will be presented in the IA are detailed in Section 17.2 *Table of Contents for Data Display Specifications*

5.2. Final Analysis

The final analysis will be conducted once all subjects have completed the study and the clinical database has been locked. Any changes made to Cohort 1 and/or 2 data after the IA may be listed if results at the final analysis lead to a different conclusion from the IA.

6. GENERAL CONSIDERATIONS FOR DATA ANALYSES AND HANDLING

6.1. General Summary Table and Individual Subject Data Listing Considerations

Summary tables and listings will be prepared according to ICH Guideline E3.

Row entries in tables are made only if data exists for at least one subject (e.g., a row with all zeros will not appear). The only exception to this rule will apply to tables that summarize the study termination status of subjects (e.g., reasons for not completing the study). In this case, zeros will appear for study termination reasons that no subject satisfied. The summary tables will clearly indicate the number of subjects to which the data apply and unknown or not performed are distinguished from missing data.

Listings will be sorted by cohort, randomized treatment group, subject number, assessment visit and date/time.

In general, missing data will not be imputed unless otherwise specified. Any imputed or derived data will be flagged in the individual subject data listings. Imputed data will not be incorporated into any raw or primary datasets. These data will be retained in derived analysis datasets.

6.2. General Post Text Summary Table and Individual Subject Data Listing Format Considerations

The tables, figures and listings will be numbered using a decimal system to reflect main levels of unique tables and listings and sub-levels of replicate tables and listings with two digits per level (e.g., Table XX.YY.ZZ. ...).

1. The first level number will be consistent with the corresponding Clinical Study Report (CSR) appendix in which the tables or listings will appear. For example, the post text tables will appear in Appendix 14 (and will be numbered 14.XX.YY) and the individual subject data listings will appear in Appendix 16 (and will be numbered 16.XX.YY). The subject disposition table will be first in the first section of the report and will be numbered Table 14.1. The supportive subject data listing will be Listing 16.1. Any subset table will have the number Table 14.1.1, Table 14.1.2, etc.
2. Table numbering will follow ICH E3 for Phase I CSRs. Subject disposition, baseline and demography and prior and concomitant medications tables should appear as the second level number (Table 14.1 series). Similar conventions will be applied to the subject data listings.
3. Each table and listing title will be complete, accurate and concise. The last line of the title will provide the analysis group being summarized (e.g., Safety Population).
4. If possible, variables being summarized, and statistics reported, will appear in the left most column of a table. The next columns for treatment formulations should report the data from left to right for the treatment formulations (i.e. Placebo, Dose Cohort 1, Dose Cohort 2, Dose Cohort 3, Dose Cohort 4 and Overall), respectively.

6.3. Data Management

All data will be recorded by the site in individual source documents. An electronic Case Report Form (eCRF) will be created by the data management group for recording of the required data in the study database. All eCRF information is to be filled in by site staff. If an item is not available or is not applicable, this fact should be indicated. Blank spaces should not be present unless otherwise directed.

The study monitor will perform source data verification of data entered into the eCRF and raise queries for correction by the site. The data entered into the eCRF will be subject to data validation checks for consistency and completeness by the data management group. Data queries will then be generated and sent to the investigational site for response before the database is locked and released for statistical analysis.

Data storage, data transfer and data cleaning will be conducted according to the relevant CNS Standard Operating Procedures (SOPs).

Derived datasets are created using SAS[®] software. Data analyses and summary tables will be generated using the currently supported version at the time of data analysis.

6.4. Data Presentation Conventions

Continuous safety variables (e.g., clinical laboratory values, vital signs and ECGs) will be reported to the same precision as the source data. Derived variables will be reported using the same precision as the value(s) from which they were derived. For the reporting of descriptive statistics, the mean and median will be reported to 1 decimal place more than the source data; the minimum and the maximum values will be presented to the same precision as the source data and standard deviations (SD) will be reported to 2 decimal places more than the source data. The coefficient of variation (CV%), as a percentage (i.e., x100%), will always be reported to 1 decimal place.

Pharmacokinetic concentration data that are presented by the lab in significant digits will be reported as received from the bioanalytical lab in by subject listings.

For categorical/discrete variables, the frequency count and the percentage (of available data) for each class of the variable will be presented and will be displayed in the form XX (XX.X%) where the percentage is in the parentheses.

Date variables will be formatted as ddMMMyyyy for presentation (where day and year are numeric and the first three letters of month in letters). Time will be formatted in 24-hour time as HH:MM for presentation.

Extra measurements (such as unscheduled or repeat assessments) will not generally be included in summary tables but will be included in subject listings. They may be used if a scheduled measurement is missing and the timing of the extra measurement is deemed suitable. They will be used in summary tables which are not 'time specific', for example, summaries of maximum post dose values. In the data listings and summary tables presented as part of the CSR, scheduled assessments will be identified by the protocol specified nominal visit day and scheduled time point.

Wherever possible, data will be decimal aligned.

The tables, figures and listings shells and table of contents as part of this Statistical Analysis Plan (SAP) provide the expected layout and titles of the tables, figures and listings. Any changes to format, layout, titles, numbering, or any other minor deviation will not necessitate a revision to the SAP, nor will it be considered a deviation from planned analyses. Only true differences in the analysis methods or data

CONFIDENTIAL AND PROPRIETARY

handling will necessitate such documentation. The appropriate listings supporting the tables will be included and are not specified in the individual sections throughout the document.

Minor modifications may be necessary to the planned design of tables, listings and figures to accommodate data collected during the actual study conduct. Any major deviations from the final approved SAP (e.g., change in the population used, change from statistical method/assumption listed, transformation of data type [e.g., continuous data transformed to categorical], exclusion of planned analysis, etc.) or additional unplanned analyses will be documented (with justification) in the CSR.

6.5. Analysis Populations

Subject inclusion into each population will be determined before database lock for the final analysis except for pharmacokinetic population which will be decided by a pharmacokinetic scientist after database lock.

6.5.1. Screen Failures

Data from screen failures will not be recorded in the eCRF. Reasons for screen failures will be collected in study screening logs.

6.5.2. Intention-to-Treat (ITT) Population

All subjects who randomized into this study, regardless of receiving the study drug (INP103 or placebo) or not, will be included in this population. In general, all data listings and subject disposition, will be generated on this population except PK and PDyn results. Summaries of demographics, prior and concomitant medications will be produced using this population.

This definition of the ITT population differs from the definition provided in the protocol and will supersede the protocol definition.

6.5.3. Benserazide Safety Population

All subjects who receive any amount of benserazide (as provided by the Sponsor) will be included in the Benserazide Safety Population. This population will be used for the analysis of the safety data collected after receiving benserazide (as provided by the Sponsor) and before receiving INP103 or placebo. This population will not be applicable to Cohort 4.

6.5.4. Safety Population

All subjects who receive any amount of INP103 or placebo will be included in the Safety Population. The data will be analyzed according to the treatment received. All safety results will be generated on Safety Population.

6.5.5. PK Population (PKP)

All subjects who receive placebo or the full planned dose of INP103 or active treatment subjects who receive partial dose (as reported by clinical observation of the number of puffs delivered) with exposure reasonably consistent with subjects who received the same actual dose amount (to be determined by clinical observation and review of data by pharmacokineticist) and have sufficient samples collected for calculation of at least one PK parameter through non-compartmental analysis will be included in the PK Parameter Population (PKP). The PK parameter data will be analyzed according to the treatment received. PK

parameter results will be produced using this population. Placebo subjects included in the PKP will only have PK parameters derived from uncorrected L-dopa concentrations.

6.6. Baseline Definition

For all safety assessments, the baseline will be defined as the last available, non-missing observation prior to first study drug (benserazide, INP103 or placebo) administration, unless specifically mentioned otherwise.

For PDyn assessment, the baseline will be defined as the last available, non-missing observation prior to first study drug (INP103 or placebo) administration, unless specifically mentioned otherwise.

In general, Unknown, Not Done, Not Applicable and other classifications of missing data will not be considered when calculating baseline observations. However, valid categorical observations will be considered for baseline calculations.

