	
5. On a stable dose of L-dopa containing medication for at least 2 weeks prior to Visit 1 (up to 1200 mg/day) with no single dose exceeding 250 mg. All other anti-PD medication (e.g. dopamine agonists [DAs], monoamine oxidase-B inhibitor (MAOB-I) or catechol-O-methyl transferase (COMT) inhibitors ARE allowed if the subject has been on a stable dose for at least 30 days prior to Visit 1.
 
6. Willing to omit their (usual) PD drugs (e.g. usual regular anti-PD medication including any L-dopa containing medication, DAs and/or COMT inhibitors and any required anti-OFF treatment) from 22:00 pm the evening prior to study dosing until 120 minutes post study treatment dosing.
 
Cohorts 1, 2 and 3 ONLY WILL take oral benserazide 25 mg on arrival at the research site (at 60 ± 5 minutes before dosing with INP103 or placebo).
 
Cohort 4 will omit oral benserazide and subjects may be dosed once OFF episode has been confirmed and all baseline assessments have been completed.
 
7. If female and of childbearing potential must agree to use adequate contraception (see Section 4.4) during the study
 
8. Able and willing to attend the necessary visits at the study centre
 
9. Willing to provide voluntary written informed consent signed prior to entry into the study
 
Exclusion Criteria:
 
 1. Severe dyskinesia (defined as per MDS-UPDRS) during a 'normal day' that would significantly interfere with the subject's ability to perform study assessments 2. In receipt of L-dopa containing medication at > 1200 mg/day 3. History of significant psychotic episode(s) within the previous 12 months in the opinion of the Investigator, or currently receiving anti-psychotic medication at a moderate dose (quetiapine >50 mg/day, risperidone >1 mg/day or olanzapine >2.5 mg/day) 4. Mini Mental State Examination (MMSE) ≤ 25 as documented within the previous 36 months or as assessed by Investigator during Screening
--	---

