Subjects may be domiciled at the clinic overnight to enable scheduled assessments on the morning of, and prior to, Visit 2 (standard medications) and Visit 3 (test article) dosing, or will have transport provided to ensure they arrive at the clinical research unit on the morning of Visit 2 and Visit 3. Regardless of time of arrival at the study site, all subjects will be required to suspend dosing of usual PD medication (e.g. regular Madopar® or Sinemet® doses, DAs and/or COMT inhibitors doses and any required anti-OFF medication [e.g. Madopar rapid]) from 22:00 pm on Day -1, the day prior to study dosing. Suspension of usual PD medication will include on the morning of Day 0.

On Day 0, upon arrival at the research site (or upon waking if the subject was domiciled overnight at the research unit), and at 60 ± 5 minutes before dosing with INP103 or placebo, all subjects in **Cohorts 1, 2, and 3** will take oral benserazide hydrochloride (benserazide) 25 mg (provided by the Sponsor). Subjects in **Cohort 4** will NOT receive oral benserazide. Subjects who arrive at the study site on Day 0 (or who were domiciled overnight) and are determined by the Investigator to be in an ON state up to the scheduled time of dosing will not be dosed and will be excluded from further study participation but may be replaced at Sponsor's discretion.

On their scheduled day of dosing (Day 0; or on arrival at the unit on Day -1), eight subjects in each of three dose cohorts (35, 70 or 140 mg of INP103 L-dopa) and at least eight (8) (maximum 12) subjects in Cohort 4 (70/7.0 mg of INP103 L-dopa:carbidopa) will be randomized in a 3:1 fashion to one of two treatment arms. All subjects in Cohorts 1, 2 and 3 will receive oral benserazide 25 mg 60 ± 5 minutes before dosing with the study drug. Subjects in Cohort 4 will not receive oral benserazide before dosing with the study drug:

- INP103 (n=6 or maximum 9 in Cohort 4)
- Placebo (n=2 or maximum 3 in Cohort 4)

[figure not shown]
Use of usual anti-PD medication (usual regular dosing [e.g. regular Madopar or Sinemet] and use of anti-OFF treatment, if required) may resume at 120 minutes after use of INP103 or placebo.

Subjects will be monitored for 7 days after the final administration of INP103 or placebo. All subjects will be observed as in-patients for at least 240 minutes post-dosing at visit 3. Follow-up evaluations will occur 7 days after dosing.

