7.2. Admission to Clinic (Day prior to Visit 2 and Visit 3)

Depending on private arrangements, capability, and logistics, subjects may be domiciled in the study clinic from the evenings prior to Visit 2 and Visit 3. Subjects will receive a standard meal and snacks and be offered a light breakfast in the morning before dosing and thereafter may be offered a standard meal and/or snacks. Subjects will not complete any study procedures until the morning of both Visit 2 and Visit 3.

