7.4. Dosing and Admission to Clinic (Day 0) (Visit 3)

7.4.1. Before Dosing

Subjects not domiciled in the study clinic on the evening of Day -1 will be transported to the study clinic as early as possible on the morning of Day 0.

All subjects, irrespective of date or time of arrival at the study clinic, will have their usual anti-PD medication (e.g. usual regular Madopar® dosing and any required anti-OFF treatment [e.g. Madopar rapid]) withheld from 22:00 on the evening before Day 0 until at least 120 minutes post-dosing with INP103 or placebo. Subjects determined as being in an ON state during the pre-dose assessments will not participate further in the study.

At visit 3, subjects will be offered, and encouraged to consume, a light breakfast, 30 minutes before dosing (and 15 minutes before pre-dose PK blood draw).

Pre-dose PK sample will be obtained once an IV cannula has been inserted, approximately 15 minutes prior to INP103 or placebo dosing. Prior to dosing, subjects will be sequentially assigned a randomization number. The subject identification number will remain the same throughout the study.

Subjects will be offered standard meal and/or snacks after dosing as appropriate.

All subjects in Cohorts 1, 2 and 3 will receive oral benserazide (25 mg) 60 ± 5 minutes before INP103 or placebo dosing.

Subjects in Cohort 4 will not receive oral benserazide but will be dosed with INP103 (with carbidopa) or placebo once OFF state confirmed and all other baseline assessments have been completed.

The following assessments will be carried out prior to dosing (in an order consistent with site's standard practice) on Day 0:

- Review to determine whether the subject continues to satisfy the study inclusion and exclusion criteria
- Vital signs (blood pressure [supine and standing]; and heart rate, respiratory rate and oral temperature [supine only])
- 12-Lead ECG
- Complete physical examination including nasal inspection
- Safety laboratory analysis sample collection (haematology, clinical chemistry and urinalysis)
- Urine pregnancy test (WOCBP only)
- Record of pre-treatment AEs (post randomization, pre-treatment emergent, including rating of dyskinesias)
- Review of the subject's concomitant medications, including non-prescription medications
- Investigator and subject self-evaluation of ON/OFF
- Full MDS-UPDRS assessment (I to IV)
- Administration of Benserazide (**60 ± 5 minutes before INP103 or placebo dosing – Cohorts 1, 2 and 3 only**)

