11.5. Vital Signs Evaluations

All individual vital signs results (supine and standing systolic blood pressure [mmHg], supine and standing diastolic blood pressure [mmHg], heart rate [beats per minute (bpm)], respiratory rate [breaths per minute] and oral temperature [°C]) will be presented in data listings. Observed vital signs parameter values and changes from baseline (prior to the first study drug administration [benserazide or INP103/placebo]) will be summarized by treatment and protocol specified collection time point.

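### The plan does not ensure a same-day safety baseline in Cohorts 1–3: a value first taken after benserazide gives way to one from Visit 1

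*SAP*

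**What the plan says.** **Baseline rule.** SAP 6.6 sets two baselines. For safety it is "the last available, non-missing observation prior to first study drug (benserazide, INP103 or placebo) administration". For pharmacodynamics the anchor is INP103 or placebo alone. SAP 11.4 to 11.6 restate the safety anchor; 11.5, for example, summarizes "changes from baseline (prior to the first study drug administration [benserazide or INP103/placebo".

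**When benserazide is taken (Cohorts 1–3).** Every statement gives 60 ± 5 minutes before dosing. Several add a second anchor. Protocol 3 says "upon arrival at the research site (or upon waking if the subject was domiciled overnight at the research unit". The synopsis version of inclusion criterion 6 says "Cohorts 1, 2 and 3 ONLY WILL take oral benserazide 25 mg on arrival at the research site". Protocol 5.1 says upon waking. SAP 4 and the SAP synopsis repeat the arrival and waking wording. Inclusion criterion 6 in Protocol 4.2 gives only the 60-minute interval.

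**Order on Day 0.** Protocol 7.4.1 lists the eligibility review, vital signs, ECG, examination, laboratory samples, ON/OFF rating, full MDS-UPDRS, benserazide and the baseline PK sample, to be done "in an order consistent with site's standard practice". Protocol 6.5.1 requires a cannula before any Visit 3 medication. For the evening before, Protocol 7.2 says: "Subjects will not complete any study procedures until the morning of both Visit 2 and Visit 3".

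**Earlier values.** Protocol Table 1 schedules vital signs, ECG, physical examination and laboratory tests at Visit 1 and at Day 0 pre-dose, but not at Visit 2.

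**Cohort 4 and placebo.** Cohort 4 takes no benserazide and is dosed once OFF is confirmed and baseline assessments are complete (Protocol 7.4.1). SAP 7.1 pools placebo subjects from all cohorts.

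**The concern.** Two sites can both comply and produce different baselines. One gives benserazide soon after arrival or waking and then takes vital signs, ECG and bloods. Under SAP 6.6 those Day 0 values cannot be baseline, and the next earlier scheduled values are from Visit 1. The other site works down the 7.4.1 list in order and gets a same-day, pre-benserazide baseline. The SAP has no rule that brings the two together and no flag to show which occurred.

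Visit 1 can be 21 days before dosing, and Protocol 4.5 permits usual Parkinson's medication then. On Day 0 that medication has been withheld since 22:00. The two baselines can therefore differ systematically in blood pressure and heart rate. Cohort 4 cannot have this problem by design, and pooled placebo can contain both kinds of baseline.

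Safety is the primary endpoint, and the primary objective is a comparison with placebo. The groups are small (6 to 9 active subjects each), so a baseline that depends on site habit can show up in the displayed mean changes.

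**Working it through.** The documents state no figure on this point, so there is none to reproduce.

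**Inputs from the documents**
- Cohorts 1–3: 6 active and 2 placebo each, so 18 active, 6 placebo, 24 in all.
- Cohort 4: 6 active and 2 placebo, or at most 9 and 3.
- Share of pooled placebo from Cohorts 1–3: w = 6/8 = 0.75, or 6/9 = 0.67.

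**Assumptions (not in the documents)**
- f: share of Cohort 1–3 subjects whose value is first taken after benserazide, from 0 to 1, the same in active and placebo.
- d: mean Visit 1 value minus mean Day 0 pre-dose value, of either sign. For blood pressure, 5–10 mmHg is used as an illustration.

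**Shift in change from baseline.** Change is post-baseline minus baseline (SAP 6.7.3). Replacing Day 0 by Visit 1 subtracts d.
- Cohort 1–3 active: −f × d
- Pooled placebo: −w × f × d
- Cohort 4 active: 0

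**Shift in active minus pooled placebo**
- Cohorts 1–3: −f × d + w × f × d = −(1 − w) × f × d = −(0.25 to 0.33) × f × d
- Cohort 4: 0 + w × f × d = +(0.67 to 0.75) × f × d

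| f | Cohort 4 v placebo | Cohorts 1–3 v placebo | Cohort 4, d = 5–10 mmHg | Cohorts 1–3, d = 5–10 mmHg |
|---|---|---|---|---|
| 0 | 0 | 0 | 0 | 0 |
| 0.5 | +0.33d to +0.38d | −0.13d to −0.17d | 1.7 to 3.8 | −0.6 to −1.7 |
| 1 | +0.67d to +0.75d | −0.25d to −0.33d | 3.3 to 7.5 | −1.3 to −3.3 |

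**Which safety measures are exposed**
- Vital signs at 30 and 60 minutes: clearly exposed, because usual medication is still withheld when they are taken.
- Vital signs at 120 minutes: less clear. A Table 1 footnote lets them run to 180 minutes, and usual medication resumes at 120.
- ECG at 120–180 minutes: may follow resumed medication (Protocol 7.4.3). The QTc-increase rows need rises above 15%, 30% or 60%; 15% of 440 msec is 66 msec, and nothing in the documents suggests a baseline shift of that order.
- Laboratory tests: the next scheduled sample is Day 7, after usual medication has resumed. A medicated Visit 1 baseline may then be the closer match.
- Treatment-emergent adverse events, QTc above 500 msec, and orthostatic hypotension (standing against supine on the same occasion): no baseline is used.
- Dyskinesia: Table 1 has no Visit 1 rating, so a rating made only after benserazide would leave baseline missing.

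**The case against.** The strongest reply is that the fallback may never happen. Protocol 7.4.1 puts benserazide second to last, after all the safety assessments, and lets sites choose the order. Cannulation before any Visit 3 medication means benserazide cannot literally be the first event after arrival. Protocol 4.2 omits the arrival wording, and the 60-minute interval appears everywhere. A site can finish its assessments, give benserazide and dose an hour later; f is then 0 and nothing shifts. This stands. A reader might infer that the plan moves the baseline of all Cohort 1–3 subjects, and of the whole placebo group, to Visit 1, or that the eligibility re-check always follows benserazide. The documents do not support that. They neither require nor forbid assessment before benserazide, and at most 67–75% of pooled placebo could be affected.

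A reader might also infer that OFF values are compared throughout with an ON baseline. ON at Visit 1 is documented only for Hoehn and Yahr staging; for vital signs and ECG it is inferred from permitted medication. As shown above, the mismatch clearly fits only the 30- and 60-minute vital signs.

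Three further points are fair. Safety is descriptive, with no inferential testing (SAP 11), so the shift is a difference between displayed means. Having separate safety and pharmacodynamic baselines is not in itself an error. The pre-benserazide anchor also looks deliberate, since the SAP treats benserazide as study drug for safety and defines a benserazide period.

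What remains is that the plan allows both outcomes and does not control which one occurs.

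**Conclusion.** The concern holds as a gap in the plan, not as a certain bias. The documents do not guarantee a same-day safety baseline in Cohorts 1–3, while Cohort 4 has one by design. Up to 24 of 32–36 subjects could be affected; the actual number depends on site practice and may differ by measurement.

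The size runs from nothing to an upper bound of 0.75d for Cohort 4 against placebo and 0.33d in the opposite direction for Cohorts 1–3. Only the placebo shares come from the documents. Both f and d are unknown, and the millimetre figures rest on the assumed d of 5–10 mmHg. The exposure lies mainly in two vital-sign time points. It is worth settling before unblinding because these change scores belong to the primary endpoint and the remedy is cheap.

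**What to change.** **SAP 6.6 and 11.4 to 11.6.** For all treatment summaries, define the safety baseline as the last Day 0 value before INP103 or placebo, in every cohort. The SAP already uses the INP103/placebo anchor for the pharmacodynamic baseline, the start of treatment-emergent events and Study Day. Keep a pre-benserazide baseline only for the benserazide-period summary. Flag any baseline that is not from Day 0.

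**Protocol.** Reconcile the synopsis inclusion criterion 6, section 3, 4.2, 5.1, 6.5.1 and 7.4.1, so that all sites follow one stated order of Day 0 assessments relative to benserazide. Which order is clinically right is not a matter for this review.

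**Cost.** SAP wording and a clarification to sites, with no new assessments. The downside is that some Cohort 1–3 baselines may be taken after benserazide while Cohort 4 baselines follow no study medicine. Protocol 1.1 states that neither decarboxylase inhibitor acts other than by inhibiting dopa decarboxylase, which suggests that this cost is small. Fixing the order alone could also give a same-day baseline if it put the assessments first, but it can help only Cohort 1–3 subjects not yet dosed. The SAP change applies to all subjects with a Day 0 pre-dose value.
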